There are approximately 107 NHS Talking Therapies providers in England, and we aimed to recruit a minimum of 26 providers (clusters). With 13 clusters per arm, assuming an intracluster correlation (ICC) of 0.027 and a baseline-endpoint correlation (r) of 0.5, we would have 84% power to detect a standardised mean difference of 0.2 (at the 5% level of significance) assuming a minimum of 100 patients per provider.

However, by May 2024, it became apparent that we were not going to be able to meet the sample size of 26 clusters. There was also concern relating to the larger-than-expected variability in cluster sizes, which would affect study power via the large coefficient of variation. Subsequently, we decided that a fixed number of patients would be randomly selected from each provider. So long as this number is not less than 200 and the coefficient of variation in cluster size did not exceed 0.3, the study would retain at least 80% power to detect a standardised mean difference of 0.2 (with the ICC and r as above) with 22 clusters.

Randomisation

As a cluster trial, allocation to either the intervention or usual care took place at the provider level, via minimisation. The minimisation factors will be:

- NHS Talking Therapies clinical performance (Recovery Rate: % of annual NHS Talking Therapy referrals for persons aged 18+ finishing a course of treatment who are 'moving to recovery'; <52 vs. ≥52)
- Site size (count of NHS Talking Therapies patients receiving low-intensity therapy; <815 vs. ≥815)
- Use of telephone delivery (pre-pandemic); ≤33% vs. >33%
- Deprivation score (IMD); <20.8 vs. ≥20.8

Minimisation factor dichotomies were chosen in order that groups would be of roughly equal size, based on data available from NHS Talking Therapies services. Allocation was undertaken sequentially and independently by Manchester Clinical Trials Unit (CTU) to maintain concealment of allocation. A random weighting element of 4:1 allowed for allocation to the group which does not minimise the imbalance between minimisation factors (i.e. a 20% chance).

Outcome Assessment

The primary outcome measure will be the Patient Health Questionnaire (PHQ-9) for depression (Kroenke et al., 2001). The PHQ-9 will be collected at baseline and at the end of treatment, via routine NHS Talking Therapies data minimum data set.

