Data on mode of intervention delivery (e.g. face-to-face, via telephone, etc.) are available and will be summarised for each treatment group separately. Data on treatment session attendance and/ or treatment completion will also be summarised by treatment group as appropriate (e.g. median; mode; range; % completing). Talking Therapies services define treatment completion as the attendance of at least two sessions recorded as either 'assessment and treatment' or 'treatment', followed by being discharged (https://www.england.nhs.uk/mental-health/adults/nhs-talking-therapies/service-standards/).

Statistical Analysis

Selection of Patients and Weighting

As per the amendment to the power calculation described earlier, for each cluster and separately for patients presenting with depression and anxiety, patients who are eligible to receive NHS Talking Therapies services will be ordered by their sex, age and date of first appointment. A simple random sample of 400 will then be drawn without replacement. Only patients whose baseline PHQ/ GAD, age and sex are not missing will be included in the sample (as it is unlikely that this information can be imputed accurately).

The sample with depression will be drawn first and 400 patients who present to each NHS Talking Therapy service (and are eligible for step 2 telephone-based psychological therapy) with mild, moderate or more severe depression (at baseline: i.e. $PHQ-9 \ge 5$) will be randomly selected to form an 'analysis sample'.

A second, non-overlapping, random sample of 400 patients with anxiety will be selected to analyse this outcome. Selection will also be based on patients who present to each NHS Talking Therapies service with mild, moderate or more severe anxiety (at baseline: i.e. GAD- $7 \ge 5$). If there are fewer than 400 patients identified for either sample, all such patients will be retained.

As NHS Talking Therapies service teams will see different numbers of patients, our primary approach will involve deriving probability weights (the inverse of the probability of being selected) in order that the patients selected at random better represent the wider population of patients seen by that particular team. We will also investigate unweighted analyses.

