We have deliberately 'over-sampled' (400 patients) as it is not known what percentage of patients will not have engaged with their NHS Talking Therapies and, therefore, have missing outcome data (post-baseline). Although we will impute any missing 'end-of-treatment' PHQ-9/GAD-7 scores (defined as the last-recorded score, acknowledging that this may not be the end of treatment per-se), the reliability of such analyses is likely to decrease with increasing amounts of missing data. For example, if 50% of end-of-treatment PHQ-9/GAD-7 scores are not available, a complete case analysis will still retain 80% power to detect the desired effect.

Descriptive Analyses

As per CONSORT recommendations (Hopewell et al 2025), we will report the number of NHS Talking Therapies services approached and the number subsequently recruited and allocated

to each arm of the trial. Reasons for declining participation in the study will be noted. The number of eligible patients (the Talking Therapy service-level mean or median number, the range and the coefficient of variation), the number of eligible patients randomly selected from each Talking Therapy service and the number of randomly selected patients from each service who have outcome data at follow-up/ treatment completion (in each trial arm) will be reported.

Outcome variables (PHQ-9 and GAD-7) and model covariates (age, sex and, if sufficiently complete, ethnicity, employment status and level of deprivation) will be described, by trial arm, for the entire population of patients in our participating Talking Therapy services (at baseline only), all sampled participants (at baseline only) and the sub-sample (of sampled participants) who provide outcome data at follow-up (at baseline and follow-up) using (as appropriate) absolute frequency/ percentage, mean/ standard deviation, median/ interquartile range, minimum/ maximum and skewness/ kurtosis. The percentage of missing data will also be reported for each variable, overall and by treatment group. Data on mode of intervention delivery (frequency and percentage of each type), treatment session attendance and components of the intervention delivered will also be summarised.

Inferential Analyses

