Null hypothesis: There is no significant difference in the severity of depression (primary)/ severity of anxiety (secondary) between patients receiving the 'enhanced telephone therapy' intervention and patients receiving usual care from NHS Talking Therapies services at the conclusion of their treatment.

Analysis Method: Analyses will be conducted using Stata (Vers.14 or later, StataCorp 2015) or R statistical software. Statistical tests will be performed with a 2-sided type I error rate of 5%. Patients will be analysed according to the trial arm to which their cluster was allocated (intention-to-treat). The analyses will be conducted following completion of treatment. It is possible that a number of patients in the database will not have completed their treatment. However, we will not know if this is the case. Therefore, we will analyse the last available data point as if it was their end of treatment. Although it may not be, this should not introduce any bias between arms.

Data on the outcome measures will be assumed to be continuous; multivariable mixed effects linear regression will be conducted (with the last recorded PHQ-9 score or the last recorded GAD-7 score as the dependent variable and the corresponding baseline values as a fixed effect covariate).

Models to be fitted: The following models will be reported. All models will include the minimisation factors and the specified covariates as fixed effects. For each proposed model, the number of participants with observed data for all variables included in the model will be reported. We will also report the adjusted difference in follow-up PHQ-9/ GAD-7 scores between trial arms (i.e. the regression parameter for trial arm), along with its 95% confidence interval and corresponding p-value.

Outcome	Model	Covariate(s)
PHQ-9/ GAD-7 at the end of treatment	0	Trial Arm Allocation only
	Α	Trial Arm Allocation
		PHQ-9/ GAD-7 at baseline
	B1 (all participants:	Trial Arm Allocation
	primary analysis	PHQ-9/ GAD-7 at baseline
	model)	Age and Sex

	B2 (subset of	Trial Arm Allocation
	participants,	PHQ-9/ GAD-7 at baseline
	equivalent to C)	Age and Sex
	С	Trial Arm Allocation
		PHQ-9/ GAD-7 at baseline
		Age and Sex
		Any Other Usable Variables *

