^{*} We will investigate the data completeness of Employment Status and Ethnicity. We will only include them in Model C above if they are at least 80% complete, as the imputation of such variables is virtually impossible. If Model C is fitted, then we will also fit Model B2 on the same subset of participants (allowing comparison). If Model C is not fitted, Model B2 will not be either.

The data structure is strictly hierarchical (patients within NHS Talking Therapies services) and, therefore, the NHS Talking Therapies service will be treated as a random effect. We will estimate regression parameters using the method of maximum likelihood (MLE). Whilst restricted maximum likelihood estimation may result in less biased parameter estimates, it is uncertain whether this approach can be used in conjunction with probability weighting (see *Selection of Patients and Weighting*). However, given the large sample size (potentially 22 x 400 = 8,800), MLE will be approximately unbiased. We will also use an unstructured covariance matrix.

Missing data at follow-up: Dependent on the extent of missing data, the method of multiple imputation (MI) by chained equations will be employed, with the extent of missing data determining how many MI datasets will be generated (as a guide, one 'imputation' per 1% of missing data, but a minimum of 10). Imputation of missing 'follow-up' values will be done separately in each arm using, as a minimum, age, sex and the baseline values of both the PHQ-9 and the GAD-7. This will be our primary modelling approach (Model B1). As a sensitivity analysis, we will also conduct an analysis of complete cases (by which we mean where outcome data are missing for a particular patient at follow-up, we will assume that it is missing (completely) at random, and we will not replace it). Such patients will, therefore, be excluded from this analysis. No subgroup analyses are planned.

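### Never-engaged patients are imputed from attenders while early leavers keep their last score, so an intervention that changes engagement can bias the primary estimate in either direction

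*SAP*

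**What the plan says.** Three rules in the SAP act together.

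- **Patients with any post-baseline score.** Inferential Analyses, Analysis Method: where treatment may be unfinished, "we will analyse the last available data point as if it was their end of treatment". The SAP adds an assurance that this will not bias the comparison of arms.
- **Patients with none.** Selection of Patients and Weighting gives the reason for over-sampling: "it is not known what percentage of patients will not have engaged with their NHS Talking Therapies and, therefore, have missing outcome data (post-baseline". Non-engagement is thus named as the cause of missing outcomes.
- **How those outcomes are filled.** Missing data at follow-up: multiple imputation "will be done separately in each arm using, as a minimum, age, sex and the baseline values of both the PHQ-9 and the GAD-7". This is the primary approach (Model B1), subject to the extent of missing data. Complete cases are the only missing-data sensitivity analysis.

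Attendance is to be described, not used in the models (Baseline Data): "Data on treatment session attendance and/ or treatment completion will also be summarised by treatment group as appropriate". The closing paragraphs of Inferential Analyses say that the intervention aims to improve engagement and could lengthen treatment. Treatment length is compared descriptively, and mediation is left outside the SAP.

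**The concern.** Take two patients in the same arm with the same age, sex and baseline scores. One attends briefly and leaves; the last score, with little time to change, is the outcome. The other never engages; the outcome is imputed from everyone in that arm with a post-baseline score, including those who had a full course. If scores fall more with more treatment, the patient who had none is credited with a better expected outcome than the one who had a little.

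The last-score rule counts leaving early as part of the outcome. The imputation treats never starting as if it carried no information beyond the baseline variables. That would matter less if both arms had the same engagement pattern. Engagement is what the intervention tries to change, so the share of patients under each rule may differ by arm, and the difference enters the treatment effect. Complete cases rest on the same assumption, so agreement between the two planned analyses would not be reassuring.

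**Working it through.** **The plan's own figure.** The SAP gives no figure for this bias. Its only yardstick is the target difference of 0.2 SD: "With 13 clusters per arm, assuming an intracluster correlation (ICC) of 0.027 and a baseline-endpoint correlation (r) of 0.5" the SAP states "84% power to detect a standardised mean difference of 0.2 (at the 5% level of significance) assuming a minimum of 100 patients per provider". With variance factor (1 - r²) × [1 + (m - 1) × ICC] = 0.75 × (1 + 99 × 0.027) = 2.755, SE = √(2 × 2.755 / 1,300) = 0.0651 and 0.2/SE = 3.07. A noncentral t with 24 df gives 83.8%, which reproduces the 84%. The power statement is not in dispute.

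**Inputs.** The rules come from the SAP. The SAP gives neither engagement shares nor score changes, so these are assumptions:

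- Control shares: p0 = 0.40 with no post-baseline score, pe = 0.15 early leavers, pf = 0.45 full course.
- PHQ-9 falls: z = 1 (never engaged), e = 1 (early), f = 5 (full).
- The intervention acts only by moving patients between groups.

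**Formulas.** Differences are intervention fall minus control fall, so positive favours the intervention.

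- True mean fall = p0·z + pe·e + pf·f
- Mean fall under the planned imputation = (pe·e + pf·f)/(pe + pf)

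Control: true 0.40 + 0.15 + 2.25 = 2.80; imputed 2.40/0.60 = 4.00.

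| 10 points of patients move | Intervention shares | True fall | Imputed fall | True difference | Planned analysis |
|---|---|---|---|---|---|
| none to early | 0.30/0.25/0.45 | 2.80 | 2.50/0.70 = 3.57 | 0 | -0.43 |
| none to full | 0.30/0.15/0.55 | 3.20 | 2.90/0.70 = 4.14 | 0.40 | 0.14 |
| early to full | 0.40/0.05/0.55 | 3.20 | 2.80/0.60 = 4.67 | 0.40 | 0.67 |
| none, split like existing attenders | 0.30/0.175/0.525 | 3.10 | 2.80/0.70 = 4.00 | 0.30 | 0.00 |

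The sign turns against the intervention only if newly engaged patients score worse, on average, than those already observed in that arm. If newly engaged patients complete treatment, the effect shrinks. If the gain is in retention, it is overstated by 1/(pe + pf) = 1/0.60, or about two-thirds.

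**Ranges.** Let z run from 0 to 2 and e from 1 to 2, with f = 5:

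- None to early: planned analysis -0.43 to -0.32; truth 0.1 × (e - z) = -0.1 to 0.2.
- None to full: planned analysis 0.11 to 0.14; truth 0.1 × (5 - z) = 0.3 to 0.5.
- Early to full: planned analysis 0.1 × (5 - e)/0.60 = 0.50 to 0.67; truth 0.1 × (5 - e) = 0.3 to 0.4.

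With half of outcomes missing, the SAP's own example (shares 0.50/0.15/0.35, falls 1/1/5), the first move gives 2.00/0.60 - 1.90/0.50 = 3.33 - 3.80 = -0.47.

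**Independent check.** A simulation of 400,000 patients per arm imputed by arm on age, sex and both baseline scores, then fitted an ANCOVA. Clustering and weights were left out, as they do not drive this bias. Control shares were 30/30/40 and falls 0/2/6. None to early gave -0.28 (truth 0.21), none to full 0.20 (truth 0.60), early to full 0.57 (truth 0.40). Complete cases gave -0.28, 0.20 and 0.56, almost the same bias.

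**Would a session count in the imputation model repair it?** Suppose early means 1 session and full means 6, and log(1 + sessions) is entered. The slope is (5 - 1)/(ln 7 - ln 2) = 3.19. At zero sessions the predicted fall is 1 - 3.19 × 0.693 = -1.2, a worsening. None to early then gives (2.50 - 0.30 × 1.21) - (2.40 - 0.40 × 1.21) = 0.22 against a truth of 0. No donor has zero sessions, so the term extrapolates.

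**The case against.** The strongest reply is that the size rests on assumptions. No document gives the score change in patients who never engage, and the null hypothesis concerns severity when treatment concludes, which is hard to define for someone never treated. A primary analysis assuming missing at random, with a planned departure from it alongside, is a legitimate choice. This stands, and a reader who infers that the planned imputation must be replaced goes further than the SAP supports: any alternative is also untestable. What fails is the second half, because the SAP plans no such departure.

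A reader might also infer that better engagement simply makes the intervention look worse. The SAP does not support that. It expressly raises longer engagement with treatment, and in that case the planned analysis overstates the benefit. Nor are non-engagers imputed only from patients who stayed: the donors include early leavers.

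The imputation list is a minimum, so more predictors could be added; none for engagement is named. The descriptive comparisons of missingness and treatment length could signal a problem but would not correct the estimate. Finally, the SAP does not say whether the baseline score comes from a session that it would count as attendance, so having no post-baseline score need not mean having had no session.

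**Conclusion.** The concern holds as a bias of uncertain direction. It follows from the SAP's own text: missing outcomes are attributed to non-engagement, the primary imputation names only baseline variables, and engagement is a target of the intervention. In the illustration, a 10-point shift displaces the estimate by -0.43 (none to early), -0.26 (none to full) or +0.27 points (early to full). At an assumed SD of 6, 0.43 points is about 0.07 SD, roughly a third of the 0.2 SD target. These sizes depend on the assumed shares and falls; the mechanism needs only that outcomes improve with attendance and that the arms differ in engagement. If engagement is the same in both arms and the intervention acts equally on all attenders, this route does not produce a false difference. The assurance that the last-score rule leaves the comparison unbiased is not justified as written.

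**What to change.** In Inferential Analyses, Missing data at follow-up:

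1. Keep the planned imputation and prespecify a second Model B1 analysis. In it, patients with no post-baseline score are imputed only from same-arm patients with a single post-baseline score, conditional on age, sex and baseline PHQ-9 and GAD-7.
2. Add a variant in which patients with no post-baseline score are assumed unchanged from baseline.
3. Report both beside the planned imputation, and call the effect robust only if the conclusions agree.
4. Do not enter log(1 + sessions) as an imputation predictor, because it extrapolates beyond the donors.

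In Analysis Method, delete the assurance that analysing the last score leaves the arms unbiased.

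In the base illustration the donor-restricted analysis recovers the truth (0, 0.40 and 0.40 for the first three moves), but only because z = e was assumed. Over the range above, it would miss by up to 0.2 points when 10 points of patients move out of the never-engaged group. That is why it belongs beside the planned analysis and not in its place.

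The cost is SAP wording, a little more analysis, and imputations that rest on a smaller donor group, so a somewhat wider interval. It needs the number of post-baseline scores per patient. The SAP does not state that this is held, but identifying a last recorded score implies it.

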Statistical Analysis Plan

Enhancing the QUality of psychological Interventions delivered by Telephone (EQUITy):

A cluster randomised trial of an 'enhanced telephone therapy' quality improvement intervention in NHS Talking Therapies

Short Title EQUITy

Trial Registration Number ISRCTN22583714

Protocol Version v11.0 (16/10/2023)

SAP Version v9.0 (21/07/2025)

Chief Investigator [name] (University of Manchester)

Health Economists [name] (University of Manchester)

[name] (University of Manchester)

Statisticians [name] (University of Manchester)

[name] (University of Manchester)

SAP Contributors [name] (University of Manchester)

[name] (University of Manchester)

Trial Design

The EQUITy trial is a two-arm, 1:1 allocation, cluster randomised, parallel-group, superiority trial (https://fundingawards.nihr.ac.uk/award/RP-PG-1016-20010). It compares Step 2 NHS Talking Therapies services (a cluster) receiving an 'enhanced telephone therapy' quality improvement intervention consisting of multiple components (service guidelines, team workshop and follow-up meetings; practitioner telephone training; resources for patients) with NHS Talking Therapies services following usual care.

The intervention has been developed to help NHS Talking Therapies services improve the quality of their telephone treatments. In the intervention clusters, staff will receive a team workshop, telephone training, educational materials to help patients understand treatments delivered by telephone and service guidelines to enhance practice. Patients will receive additional resources such as a leaflet introducing telephone treatment, an appointment card and a poster.

Patients in usual care will continue to receive routine NHS Talking Therapies care (routine telephone therapy).

Objectives

The primary objective is to assess the clinical effectiveness of the intervention:

Does the EQUITy intervention improve the mental health outcomes of patients compared to usual NHS Talking Therapies care?

A secondary objective relates to cost effectiveness:

Does the EQUITy intervention improve the cost-effectiveness of treatment compared to usual NHS Talking Therapies care?

Sample Size and Power

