Alternative tests if distributional assumptions are violated: The distribution of the responses to the PHQ-9 and GAD-7 will be examined, prior to conducting the regression analyses, via a histogram and summary statistics. If the absolute value of the skewness exceeds 1 or the kurtosis falls outside the range 2 to 4, we will consider it to be non-normal and p-values will be validated using a non-parametric bootstrapped estimate of the standard error. A randomly generated seed will be used as a starting point for the bootstrapping process and 1,000 replications will be generated. One consideration here is that some statistical software does not permit bootstrapping in conjunction with probability weighting. If this is the case, it may be necessary to rely on the properties of large samples and assume that the sampling distribution of the mean is, in fact, normal (and that bootstrapping is not required). If the skewness is in a positive direction, we will also consider modelling a logarithmic transformation of the outcome. If a satisfactory transformation cannot be found, categorisation of the PHQ-9 and/ or GAD-7 will be considered.

The focus of our intervention will be on improving patient outcomes and engagement among those offered telephone treatments. However, there is a risk that our intervention will affect the types of patients who are offered telephone treatment in intervention sites, compared to controls. We will conduct a range of robustness checks to assess any potential impact, including exploring interview data with professionals to understand changes that might have been implemented and a comparison of the types of patient referred for telephone-treatment

before and after the intervention (via comparison of the baseline characteristics, such as depression/ anxiety severity, of patients in the intervention and usual care groups).

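### The bootstrap that is to validate the p-values names no resampling unit; if patients rather than services are resampled, the check leaves out between-service variation and would confirm almost any significant result

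*SAP*

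**What the plan says.** The SAP describes a "two-arm, 1:1 allocation, cluster randomised, parallel-group, superiority trial" in which "allocation to either the intervention or usual care took place at the provider level, via minimisation" (Trial Design; Randomisation). Under Inferential Analyses the data are treated as hierarchical and "the NHS Talking Therapies service will be treated as a random effect". Estimation is by maximum likelihood, supported by an appeal to a potential 22 x 400 = 8,800 patients. All models include the four minimisation factors, and Model B1 with multiple imputation is primary.

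Under the paragraph on violated distributional assumptions, scores count as non-normal if absolute skewness exceeds 1 or kurtosis lies outside 2 to 4. In that case "p-values will be validated using a non-parametric bootstrapped estimate of the standard error". The paragraph fixes the number of replications (1,000) and a randomly generated seed. It does not give the resampling unit, say whether resampling is within arm, or say how the bootstrap combines with multiple imputation. If the software cannot bootstrap with probability weights, the analysis may instead "rely on the properties of large samples and assume that the sampling distribution of the mean is, in fact, normal", with no bootstrap.

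**The concern.** The arm effect in this trial is a contrast between two groups of services. Its uncertainty comes mainly from how services differ, and only secondarily from how patients within a service differ. A bootstrap that redraws patients keeps the same services in every replicate, so the between-service part never varies and never enters the bootstrap SE. Refitting the mixed model in each replicate does not restore it.

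Two analysts could therefore both follow the SAP and obtain standard errors that differ by a factor of about 2.6 to 3.5. The smaller one would appear to confirm the model's p-value while testing nothing relevant to a cluster trial.

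The fallback raises a different question: which sample is large enough for the normal approximation? For the arm effect the relevant count is 22 services.

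**Working it through.** **Inputs.** From Sample Size and Power: "assuming an intracluster correlation (ICC) of 0.027 and a baseline-endpoint correlation (r) of 0.5", 22 services, and at least 200 patients per service with a coefficient of variation (CV) of at most 0.3. From Selection of Patients and Weighting: 400 sampled per service; if half lack an outcome, 200 remain. Tests are two-sided at 5%. Allocation is 1:1, so 11 services per arm.

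**The SAP's own power figures.** Design effect DE = 1 + ((1 + CV²)m − 1) x ICC; variance multiplier DE x (1 − r²); power from the noncentral t on (services − 2) df.
- 26 services of 100: DE = 1 + 99 x 0.027 = 3.67; multiplier 2.755; SE = sqrt(2 x 2.755/1,300) = 0.065; power 83.8%. The SAP states "84% power to detect a standardised mean difference of 0.2".
- 22 services of 200, CV 0.3: DE = 1 + 217 x 0.027 = 6.86; multiplier 5.144; SE = sqrt(2 x 5.144/2,200) = 0.068; power 79.4%, against at least 80% stated.

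The inputs are therefore read as the SAP intended.

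**SE with and without between-service variation (CV 0).** Correct variance = (2/11)(0.027 x 0.75 + 0.973 x 0.75/m). Patient resampling keeps only the second term.

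| Patients per service | Between-service term | Within-service term | Correct SE | Patient-bootstrap SE | Ratio |
|---|---|---|---|---|---|
| 200 | 0.02025 | 0.00365 | 0.066 | 0.026 | 39% |
| 400 | 0.02025 | 0.00182 | 0.063 | 0.018 | 29% |

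The between-service term is 0.02025/0.02390 = 85% of the total at 200 and 0.02025/0.02207 = 92% at 400.

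**As a check on the model p-value.** An estimate exactly at z = 1.96 with the correct SE would show z = 1.96/0.391 = 5.0 at 200 patients, or 1.96/0.287 = 6.8 at 400. The check could hardly fail.

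**As a stand-alone test.** Type I error = 2(1 − Φ(1.96 x ratio)): 2(1 − Φ(0.766)) = 44% at 200 and 2(1 − Φ(0.563)) = 57% at 400. A simulation of 22 services of 200 (1,500 trials, 200 resamples each, no baseline adjustment) gave a true SE of 0.077, a patient-bootstrap SE of 0.030 and 44% rejection. For an assumed ICC range of 0.01 to 0.05 at 200 patients, the formula gives 26% to 56%.

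**Resampling services within arm.** In the same simulation the mean SE was 0.072 and rejection about 8% with a 1.96 cut-off. In simulations of service means that also fitted four binary factors, rejection was about 5–6% with 1.96 and 3–5% with t on 16 df.

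**Fallback.** Approximate the maximum likelihood SE as sqrt((22 − p)/22) of the correct value, where p counts service-level parameters, and use a 1.96 cut-off.
- p = 2 (intercept, arm): ratio 0.953; type I error on t with 20 df = 8%.
- p = 6 (plus four factors): ratio 0.853; type I error on t with 16 df = 11%.

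Using t on 16 df (critical value 2.12) for p = 6 moves the effective cut-off from 1.67 to 2.12 x 0.853 = 1.81, or about 9%. It therefore removes part of the excess. The remainder is the downward bias of the maximum likelihood SE itself.

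**The case against.** **The SAP does not say that patients are resampled.** This is correct. The SAP recognises the hierarchy and powers for the ICC, so a careful analyst might well resample services. The point is an omission that permits a wrong reading. A reader might infer that the SAP prescribes a patient-level bootstrap; the text does not support that.

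**The bootstrap only validates.** This is also correct. Nothing says that its p-value replaces the model's, so a reader who takes 44% or 57% as the trial's type I error goes too far. A bootstrap SE that is too small makes the check uninformative; it does not raise the error rate of the mixed-model test.

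**The fallback does not share the fault.** A reader might infer that it also drops clustering. It does not, because without a bootstrap the SE comes from a model with a service random effect. That the large sample in question means patients is itself an inference: the paragraph does not say which count it means, and the 8,800 is cited elsewhere in support of maximum likelihood.

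**Resampling services does not make a command accept weights.** This is true of packaged commands; a hand-coded loop largely avoids the problem. Weights are constant within a service for the PHQ-9 sample. That should not be claimed for GAD-7: its sample is drawn second without overlap, so patients eligible for both samples can have selection probabilities different from those eligible only for the second.

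**The step is conditional.** The SAP gives no outcome distribution, so how likely the trigger is cannot be judged.

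**Conclusion.** The concern holds as a gap in specification that should be closed. On one compliant reading, the validating SE is 39% (200 patients per service) or 29% (400) of the correct value, and the check would endorse almost any significant model result. The stand-alone rejection rates of 44% and 57% describe the worst case under that unstated reading. The fallback is a separate and lesser weakness, with roughly 8–11% type I error, because its approximation rests on 22 services.

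These figures assume the SAP's ICC and r, equal service sizes, 11 services per arm and equal weighting of services. The fallback figures also use a simple approximation to the maximum likelihood bias. Unequal weights and imputation were not modelled.

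**What to change.** State in the SAP that:
- whole services are resampled with replacement within each arm, keeping each service's patients and their own weights together and giving a repeated service a new identifier each time;
- Model B1 is refitted in each replicate, with singular replicates discarded and their number reported (about 0.3% in one simulation with the four factors);
- the order of bootstrap and multiple imputation is fixed in advance;
- the bootstrap is coded as a loop, so that limits on weights in packaged commands do not force the fallback;
- if the fallback is still used, the model estimate is referred to a t distribution with service-level df (22 − 6 = 16 after intercept, arm and four minimisation factors), without reliance on large-sample normality. This removes only part of the excess, so the report should acknowledge the remaining maximum likelihood bias.

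Any statement that weights are constant within a service should be limited to the PHQ-9 sample.

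The cost is a few sentences and a short piece of code, more computing if imputation is repeated within replicates, and a slightly less favourable p-value.
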